1 STUDY OBJECTIVES

1.1 Primary Objectives (1a and 1b)

This study will examine the feasibility of a SNF-PC intervention in persons with Alzheimer's and related dementias (ADRD) and cognitive impairment (MCI) and address patient/caregiver reported outcomes including quality of life, symptom management, and satisfaction.

1a: Establish the feasibility of the SNF-Palliative Care (PC) intervention, determined by: (1) percentage of all post-acute SNF patients with ADRD/CI who meet eligibility criteria; (2) percentage of eligible patients with ADRD/CI and legally authorized representatives (LAR)/surrogate decision makers (also called a caregiver) who participate in the study; (3) percentage of participating patients with ADRD/CI who receive the SNF-PC and from whom all data are collected; and (4) clinician fidelity to the SNF-PC protocol (defined as 90% adherence to protocol elements).

1b: Measure patient/caregiver reported quality of life, symptom management, and satisfaction with care post SNF-PC in a two-arm non-randomized controlled pilot clinical trial among 50 patients with ADRD/CI.

1.2 Secondary Objectives (2)

This study will compare the demographics, clinical characteristics, and palliative (PC) needs of people with ADRD/CI versus non ADRD/CI serious illnesses during post-acute SNF care in NHs.

2 BACKGROUND AND RATIONALE

2.1 Background on Condition, Disease, or Other Primary Study Focus

Alzheimer's disease and related dementias (ADRD) are serious, life limiting illnesses with no known cure. ADRD are often underdiagnosed in older adults yet cognitive impairment (CI) is often an early/middle stage of the dementia continuum with about one third of older adults with mild cognitive impairment developing dementia within 5 years.¹ Dementia is the fifth-leading cause of death in older adults² and the majority of people with advanced dementia die in nursing homes (NHs).³ Miller et al reported that 40% of U.S. NH residents dying with advanced dementia received Skilled Nursing Facility (SNF) care in the last 90 days of life, and receipt of this care was associated significantly with poorer end-of-life outcomes, including a higher risk of dying in a hospital, compared to decedents with no SNF care.⁴ SNF care is a Medicare post-acute rehabilitation service delivered in NHs focused on intense rehabilitation and/or aggressive, disease-modifying therapies. Regardless of life expectancy, use of SNF care precludes access to Hospice services.^{5,6} Palliative care (PC) offers an evidence-based alternative.⁷

2.2 Study Rationale

PC offers an approach to improve care for older adults with ADRD in SNFs.^{7,8} Key components of PC are: 1) open discussion of illness trajectories, and establishment and communication of patient- and family- directed goals that guide health care; 2) aggressive prevention, early identification and treatment of illness-related symptoms; and 3) identification of psycho-spiritual needs and approaches to mitigating suffering.^{9,10} PC interventions are associated with improvements in patient quality of life and symptom burden.⁹⁻¹² There is evidence that PC for persons with ADRD can increase advance care planning and improve patient and caregiver satisfaction.¹²

The evidence-based SNF-PC encounter is a multi-component non-pharmacologic primary care provider delivered intervention designed to meet the PC needs of persons living with dementia (PLWD) receiving post-acute care in NHs. Components focus on assessing and managing symptoms, conducting and documenting goals of care conversations, communicating needs, recommendations, and treatment preferences of the NH team members.

3 STUDY DESIGN AND DURATION

3.1 Design

The study team will conduct a two-arm non-randomized controlled pilot clinical trial enrolling 50 persons with ADRD/CI who are in post-acute SNF NH care to meet the study objectives.

3.2 Enrollment Numbers

We anticipate screening up to 150 participants. Up to 50 patients with ADRD/CI admitted to 11 SNF NHs owned and/or operated by Acts Retirement Life Communities (“Acts”) will be enrolled.

3.3 Study Duration

Participants will be enrolled in the study for up to a total of 21 days.

3.4 Compensation

N/A

4 SELECTION AND ENROLLMENT OF PARTICIPANTS

4.1 Key Inclusion Criteria

Patients: **1)** admitted for SNF post-acute care at a participating NHs following a recent hospitalization, **2)** age \geq 60 years old, **3)** speaks English (if verbal), **4)** if non-verbal/unable to participate in a conversation and/or unable to make decisions, has a legally authorized representative (LAR)/surrogate decision maker who can make decisions for the patient as determined by Acts staff, **5)** documented ADRD or CI (BIMS \leq 12) diagnosis in the medical record, **6)** at least one global indicator for PC at SNF admission (provider would not be surprised if patient died within 1 year, believes the patient would benefit from advance care planning or symptom management; frequent hospital or NH SNF admissions; complex care requirements; decline in function; feeding intolerance; unintended decline in weight; or previous hospice assessment or enrollment and subsequent discharge).

Surrogate/LAR: **1)** \geq 18 years old; **2)** family member or friend of an eligible patient as determined by Acts staff; **3)** speaks English

4.2 Key Exclusion Criteria

Patients: **1)** who have previously received or are referred for PC by their primary care team, **2)** with a discharge plan within 48 hours of screening, **3)** currently receiving hospice care, **4)** who do not have one global indicator of need, **5)** not recently hospitalized, **6)** not diagnosed with ADRD/CI (BIMS \leq 12), **7)** $<$ 60 years of age, **8)** that are non-English speaking, (if verbal) and **9)** if unable to make decisions, do not have an LAR/surrogate decision maker.

Surrogate/LAR: **1)** < 18 years of age, **2)** not a family Member or friend of an eligible patient, **3)** non-English speaking

4.3 Study Enrollment Procedures

UMB study team members will email designated points of contact at Acts at designated times that are predetermined and convenient for Acts staff weekly (this will vary based on their schedules). Study team members will then call the designated points of contact at each Acts site to receive new SNF unit admissions each week using the Screening Script for Acts. The study team will attempt to recruit all residents who meet inclusion criteria. The study team member will then contact designated Acts staff to screen and review medical records using the inclusion criteria to determine eligibility remotely. The research staff will not be cold calling potential participants. Acts staff will not be engaged in the research.

Global indicator of need: Acts staff will be given a copy of these forms to review medical records remotely with research staff. The purpose of this form is to confirm if the resident has at least one global indicator of need. If the resident is found to not have a global indicator of need, they will be excluded from the study. Those who meet these criteria will be contacted for enrollment into the study.

Once the study team has the list of eligible residents from the facility, they will contact potential participants (eligible patients or the LAR/surrogate decision makers of eligible patients) by phone and read the broadcast notification with the option to opt out. If they decide they want to enroll, study team members will arrange a convenient time to administer the baseline Palliative Care Outcome Scale version 2 (POSv2), Satisfaction with Care at the End of Life in Dementia (SWC-EOLD, and the Symptom Management at the End of Life in Dementia (SM-EOLD) with each patient or LAR/surrogate decision maker.

If patient names are provided by Acts, study staff will ensure they are recorded separate from the primary database and are used only for the necessary amount of time to complete enrollment after which the record will be erased/destroyed.

5 INTERVENTION

5.1 Palliative Care Encounter Intervention (STANDARD OF CARE)

Subjects will receive usual care plus a SNF-PC Encounter (intervention) by existing Acts providers who have been provided evidence-based PC focused training that includes ADRD/CI components. The goal of the intervention, the SNF-PC Encounter, is to evaluate illness understanding, symptom assessment and management, goals of care conversations, documentation, communication, and implementation recommendations. While the intervention is not specifically designed for patients diagnosed with ADRD/CI, all components are consistent with appropriate care for persons with cognitive impairment and their LAR/surrogate decision maker and include some ADRD/CI specific components. The intervention will be administered by Acts providers who have been trained to conduct the SNF-PC Encounter.

5.2 Handling of Study Interventions

A standardized treatment manual will guide the general approach for the Acts providers delivering the SNF-PC Encounter.

6 STUDY PROCEDURES

6.1 Research Procedures

In this pragmatic clinical trial, broadcast notification will be utilized to inform all newly admitted patients at each study site of their participation in this trial. During the admission process, potential subjects will be provided with a 1-page summary sheet (Broadcast notification) detailing their participation in this study that will include contact information for the study team, should the subject or their LAR/surrogate decision maker elect to opt-out of participating. Baseline data will be collected virtually via telephone by asking each newly admitted patient or their surrogate to complete the Patient Outcomes Scale (POSv2), the Satisfaction with Care at the End of Life in Dementia (SWC-EOLD), and the Symptom Management at the End of Life in Dementia (SM-EOLD).

Between 14 days and 21 days after the baseline POSv2, SWC-EOLD, and the SM-EOLD are administered, all subjects will be asked to complete the POSv2, SWC-EOLD, and the SM-EOLD again virtually via telephone. The POSv2, SWC-EOLD, and the SM-EOLD will be given a total of two times to those in the INTERVENTION and CONTROL groups (at baseline and follow up (14-21 days later)).

Deidentified subject demographics will be collected on all participants in the following way: Study team members will review subject's medical records and enter de-identified data into a Research Electronic Data Capture (REDCap) database (Acts staff assists with the study team's access to subject's medical record).

The goal of the intervention is to prevent, identify and treat symptoms early during SNF care, establish goal directed treatment decisions, and support the patient and family in decision making. We anticipate that many Palliative Care encounters involve a single encounter with the patient and/or LAR/surrogate decision maker, but we have made allowances for follow up visits depending on individual patient and family needs (e.g., symptom management, continuing goals of care discussions). We will use usual care as the control condition. Usual care consists of traditional resources focused on skilled nursing care without services to support specialty palliative care. A usual care comparison will test whether the Palliative Care Encounter improves patient/family reported outcomes compared to traditional services. We have chosen to not use an attention control condition because the goal of this pilot clinical trial is to assess feasibility and determine the effect size of the intervention on the primary outcome.

Study team members will collect measures via phone or through a secured online template to minimize missing data at two time points (baseline and 14-21 days later) during the study. All data will be entered and managed in REDCap by the RA, project manager, or the PI.

Patient/Caregiver Quality of Life: Measured at baseline and follow-up (14-21 days later), the Palliative Outcomes Scale version 2 (POSv2) is a 12-item survey that measures quality of life in five dimensions: 1) physical; 2) emotional; 3) psychological; 4) spiritual needs, and 5) provision of information and support. (RESEARCH PROCEDURE)

Satisfaction With Care at the End of Life in Dementia (SWC-EOLD): Measured at baseline and follow-up (14-21 days later), the SWC-EOLD is a validated, 10-item scale that measures satisfaction with care for PLWD. Each item is measured on a 4-point Likert scale ranging from 1 (“strongly disagree”) to 4 (“strongly agree”) and uses a “prior 90 days” timeframe. Specific elements include satisfaction with medical and nursing care, decision-making, and their understanding of illness. All items are summed, yielding a range of scores of 10-40. Higher scores indicate greater satisfaction. (RESEARCH PROCEDURE)

Symptom Management at the End of Life in Dementia (SM-EOLD): Measured at baseline and follow-up (14-21 days later), the SM-EOLD is a valid and reliable 9-item scale that measures PLWD physical and psychological symptoms over the previous 90 days. Each item is rated on a 6-point Likert scale ranging from 0 to 5 (0 = “daily”, 1 = “several days a week”, 2 = “once per week”, 3 = “2 or 3 days a month”, 4 = “once a month”, 5 = “never”). Scores are summed and range from 0 to 45 (higher scores indicate better symptom management). (RESEARCH PROCEDURE)

Palliative Care Encounter: Trained provider will discuss illness trajectories, establish, and communicate patient-directed goals that guide health care decisions, identify and treat illness-related symptoms, and identify psycho-spiritual needs and approaches to mitigate suffering. (STANDARD OF CARE)

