9.4 Data Analyses

We will establish the feasibility of the SNF-PC intervention in persons with ADRD/CI using established benchmarks based on published recommendations for evaluating pilot studies. We will track the number of eligible patients, monitor follow-up, document rates of eligibility, enrollment, and completion of the intervention, and collect the outcome measures with <5% missing data. We will determine clinician fidelity to the SNF-PC protocol

We also will estimate the effect size of the SNF-PC intervention on pre-post changes in the POSv2, SWC-EOLD, and the SM-EOLD relative to the control group. These estimates will be summarized with two-sided 90% Confidence Intervals and p-values corresponding to tests against the null hypothesis of no (zero) difference.

We also will examine the demographics, clinical characteristics, and palliative care needs of people with ADRD/CI versus non ADRD/CI serious illnesses during post-acute SNF care. As the

comparisons will be made using baseline/pre-intervention information, all 50 participants enrolled in this study are potentially includable in the analysis.

The primary analysis will be to compare the mean pre-post changes in the POS v2 between the intervention and control arms. Linear regression models will be used to compare the two groups. The within-arm changes and differences between arms will be summarized with two-sided 90% CIs and p- values corresponding to tests against the null hypothesis of no (zero) change or difference. We will also explore subgroup effects of the intervention on endpoints by testing for statistical interactions between the binary group indicator and covariates of interest such as sex, age, and race.

Other key parameters needed to plan a follow-up study will be estimated as well, including the standard deviation (SD) and intraclass correlation coefficient (ICC) of each endpoint. The ICC summarizes the degree of correlation of values among patients within a site, which is an important parameter when planning a future cluster randomized controlled trial.

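### Cognitive severity, diagnosis type and the need indicators seen at screening are not named as analysis data, and the non-randomised POSv2 comparison has no planned adjustment or baseline table by arm

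*Combined protocol and SAP*

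**What the plan says.** **Chart data.** Section 6.1 introduces the chart review with "Deidentified subject demographics will be collected on all participants in the following way". It then says that study staff will "review subject's medical records and enter de-identified data into a Research Electronic Data Capture (REDCap) database". It gives no field list. Table 3 in section 6.5 lists only POSv2, SWC-EOLD and SM-EOLD.

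**What screening sees.** Section 4.1 requires ADRD, or CI defined by BIMS of 12 or less, as a "diagnosis in the medical record", plus at least one global indicator for palliative care. Under section 4.3, study staff "contact designated Acts staff to screen and review medical records using the inclusion criteria to determine eligibility remotely". Of the global-indicator form, 4.3 says "The purpose of this form is to confirm if the resident has at least one global indicator of need".

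**What is to be analysed.** Section 1.2 states "This study will compare the demographics, clinical characteristics, and palliative (PC) needs of people with ADRD/CI versus non ADRD/CI serious illnesses". Section 9.4 repeats this without listing variables.

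**Design and model.** Section 3.1 states "The study team will conduct a two-arm non-randomized controlled pilot clinical trial", and section 9.2 confirms that there is no randomisation. Section 9.4 makes the between-arm difference in mean POSv2 change the primary analysis, using linear regression. The only covariates it names are "covariates of interest such as sex, age, and race", and those are for subgroup interaction tests.

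**The concern.** Without randomisation, nothing in the design balances the arms on severity. The entry criteria admit a wide range: documented ADRD or CI by BIMS score, and anything from one indicator to many. The indicators include decline in function, unintended weight loss, frequent admissions and past hospice contact, all of which could plausibly relate to change over 14 to 21 days.

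If the arms differ on these items and the items are not in the dataset, the imbalance cannot be seen or adjusted for. It goes straight into the effect estimate, in either direction. Section 6.1 says the pilot is meant to determine the effect size, so a biased estimate would carry into the planning of the follow-up study. Section 11 calls for records to be destroyed as soon as possible after analysis, so values not recorded during the study may be hard to recover later.

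**Working it through.** **Step 1. Trace each item from screening to analysis.**

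| Item | Seen at screening | Named as analysis data | Used in 9.4 |
|---|---|---|---|
| BIMS score | 4.1 (threshold) | nowhere | no |
| ADRD versus BIMS-only CI | 4.1 | nowhere | no |
| Individual global indicators | 4.1, 4.3 | nowhere | no |
| Demographics | age only (4.1) | 6.1 | interactions only |
| POSv2, SWC-EOLD, SM-EOLD | no | 6.1, 6.3, Table 3 | as change scores |

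Every participant must have ADRD or CI, so the yes/no diagnosis cannot separate the arms. The BIMS value, the type of diagnosis and the individual indicators can.

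**Step 2. Reproduce the plan's own figures.** Section 9.2 gives an SD of pre-post change in SWC-EOLD of 4.9 and 22 completers per arm. No SD is given for POSv2.
- Power for a 2.7-unit within-group change, one-sample t-test, two-sided alpha 0.10: 80.4% (plan: 80%).
- Between-arm SE = 4.9 × √(2/22) = 1.477. With t(0.95, 42 df) = 1.682, the 90% half-width is 1.682 × 1.477 = 2.48 (plan: 2.5), or 2.48/4.9 = 0.51 SD.

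**Step 3. Illustrate the bias.** All inputs here are assumptions. Let severity correlate ρ with change, and let the arms differ by d SD on severity. Then bias = ρ × d in SD units, or ρ × d × 4.9 in SWC-EOLD units. The false-positive rate comes from the noncentral t distribution with 42 df and noncentrality bias/1.477.

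| ρ | d | Bias (SD) | Bias (units) | False-positive rate (nominal 10%) |
|---|---|---|---|---|
| 0.1 | 0.25 | 0.025 | 0.12 | 10.1% |
| 0.1 | 0.5 | 0.05 | 0.25 | 10.5% |
| 0.3 | 0.5 | 0.15 | 0.74 | 14.0% |
| 0.3 | 1.0 | 0.30 | 1.47 | 25.7% |

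The last row is 1.47/2.48 = 59% of the half-width. The results in SD units are the ones that carry over to POSv2.

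**Step 4. Cost in precision of two covariates.** Residual df fall from 42 to 40, and t(0.95, 40 df) = 1.684. If the covariates remove a share R² of the residual sum of squares and one of them differs by d SD between arms,

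half-width = 1.684 × 1.477 × √(42/40) × √(1 − R²) × √(1 + d²/4).

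| d | R² = 0 | R² = 0.09 |
|---|---|---|
| 0 | 2.55 | 2.43 |
| 0.5 | 2.63 | 2.51 |
| 1.0 | 2.85 | 2.72 |

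Where adjustment matters most, it widens the interval from 2.48 to about 2.5 to 2.85, at most about 15%.

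**The case against.** The strongest reply is that this is silence about detail in a 50-patient feasibility pilot. Three stronger readings that a reader might draw do not stand.

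- **That only demographics are stored.** Section 6.1 also says that de-identified data from the medical record are entered, without limit, and 9.4 commits to examining clinical characteristics from baseline information. The chart review may well be meant as their source. The yes/no wording in 4.3 concerns the indicator form, not BIMS or diagnosis. What can be said is that no clinical field is named.
- **That the arms cannot be compared on severity at all.** Baseline POSv2 and SM-EOLD are collected in both arms and measure palliative need and symptom burden. The linear regression in 9.4 does not exclude covariates.
- **That objective 1.2 has no data.** It has no defined clinical variables, which is a narrower statement.

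The size is also open to challenge. The correlation and the imbalance are assumed; the r = 0.3 in 9.2 is a pre-post correlation, not one between severity and change. The weaker inputs leave the error rate at about 10%. A count of indicators is not a validated severity scale, since it mixes provider opinion, admissions history and functional decline.

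These replies narrow the point without removing it. The baseline scales do not measure cognition, diagnosis type or the prognostic indicators, and 9.4 commits to no baseline comparison by arm and no adjusted model, even with the scales it does collect.

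**Conclusion.** The concern holds in limited form. The plan names only demographics for chart extraction and does not say that the BIMS score, diagnosis type or individual indicators are kept. It compares non-randomised arms on POSv2 change without a stated adjustment or baseline table. Followed as written, comparison or adjustment could use only demographics and baseline scale scores, and the plan prespecifies neither.

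The consequence may be negligible or material: 0.025 to 0.30 SD (0.1 to 1.5 SWC-EOLD units), with a false-positive rate of about 10% to 26%. This rests on the assumed ranges (ρ 0.1 to 0.3, d 0.25 to 1.0 SD) and on the SWC-EOLD SD standing in for an unstated POSv2 SD. The plan's stated power and between-arm precision reproduce and do not depend on this gap. The change should be made because the remedy is cheap, not because a large bias has been shown.

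A reader might infer that keeping these fields would also complete objective 1.2. It would not: they describe only the ADRD/CI side, and every enrolled patient is on that side, so the non-ADRD/CI comparator is still missing.

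**What to change.** 1. **Section 6.1 (and Table 3).** List as REDCap fields for every enrolled patient: BIMS score, with a level for patients who could not be tested; documented ADRD versus CI by BIMS only; and each global indicator ticked. If these are already captured, one sentence saying so is enough.
2. **Section 9.4, baseline table.** Tabulate these fields and the three baseline scale scores by arm.
3. **Section 9.4, model.** Prespecify one adjusted between-arm POSv2 analysis with a small covariate set, for example BIMS and number of indicators, and report it beside the planned comparison. State how patients without a BIMS score enter the model. With about 44 completers the set should stay short.
4. **Objective 1.2.** Use the same fields to define the clinical characteristics of the ADRD/CI group, and state separately where the non-ADRD/CI comparator comes from.

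**Cost.** A few fields from records already reviewed at screening, one table and one more model. The adjusted analysis uses 2 degrees of freedom, and its interval may be wider than the planned one if the arms are imbalanced. Reporting both results lets the reader see that trade-off.
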